#### **2.2.2. Exclusion criteria**

Patients on dialysis will be excluded because of possible metabolic features. Individuals with paresis of the lower limbs or hemiparesis due to a stroke will be excluded because of neurological involvement that can influence the results. Hypo- or hyperthyroid patients will be excluded because of the role of thyroid hormones in muscle homeostasis. Pitting oedema of the legs (due to heart failure, anasarca oedema, renal failure or liver cirrhosis) or severely dehydrated patients will be excluded because fluid shifts could influence the ultrasound measurement results. Because of possible previous changes in muscle mass, architecture and function, patients with systemic connective tissue disorders, myositis, calcification and ossification of muscle, systemic atrophies primarily affecting the central nervous system and demyelinating diseases of the central nervous system will be excluded. Patients using chronic oral corticosteroids will be excluded.

#### **2.2.3. Settings and locations**

The study will be a multicenter study held in different university and tertiary teaching hospitals throughout Europe.

## 2.3. Measurements

### 2.3.1. Patient characteristics

Date of birth, gender, height and weight will be registered. If the patient is bedridden, weight can be measured through either weight chairs or weight measuring lifts. Height will be estimated using the ulna length or knee height [20]. Date of admission and discharge will be noted. The home care setting of the patient will be registered. The main reason of hospital admission will be registered.

Comorbidities on admission will be registered through the Cumulative Illness Rating Scale for Geriatrics (CIRS-G) [21]. The CIRS-G was designed to estimate the survival of elderly persons, assessing disease severity using a score from 0 to 4 in 14 different categories of organ systems: cardiac, vascular, hematological, respiratory, ophthalmological and otorhinolaryngological, upper gastro-intestinal, lower gastro-intestinal, hepatic and pancreatic, renal, genito-urinary, musculoskeletal and tegumental, neurological, endocrine/metabolic/breast and psychiatric [22]. Score '0' stands for 'no problem affecting that system', score '1' stands for 'current mild problem or past significant problem', score '2' stands for 'moderate disability or morbidity', score '3' stands for 'severe problem' and score '4' stands for 'extremely severe problem'.

Laboratory values that will be checked are either nutritional through albumin and prealbumin, inflammatory through C-reactive protein (CRP) and white blood cell count, and the measurement of 25-hydroxyvitamin D (25-OH-vitamin D). Blood samples will be collected on day of admission. Laboratory values that are not expected to fluctuate strongly (albumin, pre-albumin, 25-OH-vitamin D) will be taken within the first 5 days of admission.

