### 1.1. Objective

The aim of this study is to investigate the effect of hospitalisation due to acute illness on muscle mass characteristics, assessed in older adults through ultrasound. The primary endpoint is the change of characteristics of muscle mass in function of time since admission. The secondary endpoint of the study is to identify health related parameters associated with the development of acute sarcopenia. Relevant determinants of the evolution of muscle

mass and muscle strength since admission (reason of hospitalisation, comorbidities and laboratory data) will therefore also be investigated.

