### 2.3.2. Muscle mass

In order to obtain reliable and consistent measurements, all ultrasonography will be done by an ultrasonographist that is trained to perform the measurements proposed. For the measurements, a linear probe of 5 cm width will be used. Frequency of the beam will be set on 12 MHz.

Patients should not have had any physical exercise in the 30 minutes before the measurement. Muscles should be completely relaxed and patients should be placed in the supine position, with hips in neutral position and knees fully extended. The dominant leg will be taken for the measurements. To calculate the relative muscle thickness values, the total length of muscle will be noted.

Ultrasonographic data of the four bellies of the quadriceps muscle (rectus femoris, vastus lateralis, vastus medialis, vastus intermedius) will be taken. Measuring points will be specified according to the propositions of the SARCUS-working group [19]. Muscle thickness, fascicle length, pennation angle, muscle cross-sectional area and echo-intensity of all muscles listed will be taken.

The first measurement will be taken as early as possible within 48 hours after admission at the latest. Follow-up measurements will be taken according to the type of ward the patient is admitted to. For patients that are expected to be hospitalized for a limited time (<5 days), the follow-up measurement will be done 3 days after initial measurement. For patients that are expected to be hospitalized for a longer time (>7 days), measurements will be repeated 7

days after initial measurement, to be repeated after another 7 days as long as the patient is hospitalized.

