### **2.3.3. Muscle strength and function**

Muscle strength will be measured through hand grip strength using a Jamar dynamometer, using the Southampton protocol [23]. The first measurement will be taken as early as possible within 48 hours after admission at the latest. Follow-up measurements will be taken according to the type of ward the patient is admitted to. For patients that are expected to be hospitalized for a limited time (<5 days), the follow-up measurement will be done 3 days after initial measurement. For patients that are expected to be hospitalized for a longer time (>7 days), measurements will be repeated 7 days after initial measurement, to be repeated after another 7 days as long as the patient is hospitalized. Measurement will be done directly after the ultrasonographic assessment. If feasible, muscle function will be measured through gait speed, using the 4-meter walking test at usual gait speed [24]. In case of those bedridden, gait speed will not be measured.

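### On the short-stay schedule, albumin, prealbumin and 25-OH-vitamin D may be drawn up to 2 days after the follow-up scan they are meant to help explain

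*Combined protocol and SAP*

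**What the plan says.** Section 2.3.1 first gives a general sampling rule: "Blood samples will be collected on day of admission". The next sentence sets a different window for three assays: "Laboratory values that are not expected to fluctuate strongly (albumin, pre-albumin, 25-OH-vitamin D) will be taken within the first 5 days of admission". CRP and white cell count are not in that exception, so they stay on the admission day.

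Section 2.3.2 times the first ultrasound: "The first measurement will be taken as early as possible within 48 hours after admission at the latest". Follow-up depends on expected stay. The short schedule reads "For patients that are expected to be hospitalized for a limited time (<5 days), the follow-up measurement will be done 3 days after initial measurement". The long one reads "For patients that are expected to be hospitalized for a longer time (>7 days), measurements will be repeated 7" days after the first. Section 2.3.3 gives grip strength the same timetable and ties it to the scan: "Measurement will be done directly after the ultrasonographic assessment".

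Section 1.1 makes the laboratory data explanatory variables. It announces an investigation of determinants of the evolution of muscle "mass and muscle strength since admission (reason of hospitalisation, comorbidities and laboratory data) will therefore also be investigated". Section 3 (Discussion) describes nutritional status at admission as recorded by MNA-SF, with selected laboratory values as a complement.

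No section requires the three samples to precede either scan, asks for the draw date, or says in section 2.4 how a late value is handled.

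**The concern.** A predictor of change should be fixed before the change is measured. If albumin or prealbumin is drawn after the follow-up scan, its value may partly reflect what happened in hospital, such as illness, fluids or feeding, rather than the state in which the patient arrived. An association with muscle loss could then run in either direction. The study could not separate the two, because section 3 says that food intake in hospital will not be recorded.

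What is at stake is the reading of three covariates in the secondary, determinant analysis. The primary endpoint, change in muscle characteristics over time since admission, uses none of them. The hypothesis on inflammation in section 1.2 is also untouched, since the inflammatory markers are drawn on the day of admission.

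**Working it through.** The plan states no figure on this point to reproduce. The check is timeline arithmetic in days since admission.

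**Inputs**
- First scan, b: 0 to 2 (section 2.3.2, 48 hours).
- Short-schedule follow-up: b + 3 (sections 2.3.2 and 2.3.3).
- Long-schedule follow-up: b + 7 (same sections).
- End of laboratory window, L: 5 (section 2.3.1).

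**Formula.** Time in the laboratory window after follow-up = max(0, L − follow-up day).

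| First scan (day) | Short follow-up (day) | Window left after it (days) | Long follow-up (day) | Window left after it (days) |
|---|---|---|---|---|
| 0 | 3 | 5 − 3 = 2 | 7 | 0 |
| 1 | 4 | 5 − 4 = 1 | 8 | 0 |
| 2 | 5 | 5 − 5 = 0 | 9 | 0 |

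On the long schedule every permitted draw precedes the first follow-up by at least 7 − 5 = 2 days. On either schedule a draw can follow the baseline scan by up to 5 days (first scan on day 0, draw on day 5). The plan gives no follow-up time for expected stays of 5 to 7 days, so that group cannot be checked.

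**How often.** The documents give no distribution of scan or draw times. As an illustration only, assume that b is uniform on 0 to 2 and the draw uniform on 0 to L. The share of short-schedule draws after follow-up is the average over b of max(0, L − 3 − b) / L.
- L = 5: the average of (2 − b) is 1, so 1/5 = 20%.
- L = 4.5: the average of max(0, 1.5 − b) is (1.5² / 2) / 2 = 0.5625, so 0.5625/4.5 = 12.5%.
- L = 4: the average of max(0, 1 − b) is (1² / 2) / 2 = 0.25, so 0.25/4 = 6.25%.

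The shorter values of L stand for a stricter reading of the 5-day window, or for discharge before day 5. A simulation of 1,000,000 draws gave 20.0%, 12.5% and 6.2%, and 0% on the long schedule.

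**After the fix.** The earliest follow-up is day 3. A draw on the admission day, or by 48 hours, leaves no overlap on either schedule.

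**The case against.** The strongest reply is the plan's own: these values are not expected to move much over a few days, so a day-4 result can stand in for the admission result. If that is right, the harm is small. The plan gives no data for it and treats the three assays alike, but the documents contain no figure that refutes it either. The size of any bias therefore stays open. The case for changing the rule does not rest on refuting the claim, because blood is already drawn on the day of admission and an admission value serves the stated purpose at least as well.

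The second reply concerns reach, and it stands. Only the short schedule is exposed. The Abstract also limits inclusion to stays of at least 5 days, a condition that section 2.2.1 and Table 1 do not repeat and that sits badly with a schedule for shorter stays. If it is enforced, the exposed group shrinks to patients expected to leave early who stay longer.

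Third, the two sentences in section 2.3.1 could be read so that the day of admission governs all samples, in which case the problem disappears. The second sentence reads more naturally as an exception.

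A reader might go further than the documents allow in two ways:
- **A 40% share of late draws.** This comes from a first scan on day 0 and draws spread evenly over days 1 to 5 (2 of 5). It leaves out the admission day. Counting days 0 to 4 gives 1 of 5 (20%), and days 0 to 5 gives 2 of 6 (33%). It is also the worst case for scan timing; for a first scan on day 2 the share is 0.
- **Missing values concentrated in the shortest stays, or timing that differs by centre.** Either is possible, but it is an inference from the windows. Nor can one patient both leave before the draw and have it on day 5.

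**Conclusion.** The concern holds for the short-stay schedule. As written, the plan permits albumin, prealbumin and 25-OH-vitamin D to be drawn up to 2 days after the follow-up scan and grip test, and nothing else in it prevents this. That follows from the stated windows and needs no assumption beyond counting the laboratory window to day 5.

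The frequency does rest on assumptions. The range of about 6% to 20% of short-stay draws depends on uniform timing and on how the window is counted, and the true share cannot be known from the documents.

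It would be wrong to infer that the determinant analysis as a whole runs backwards in time. Patients on the long schedule have no draw after follow-up, though a draw may come days after their baseline scan. Severity is minor to moderate: three covariates of a secondary endpoint, in one schedule, with a cheap repair.

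**What to change.** Change section 2.3.1 so that the three assays are run on the admission-day sample already taken for CRP and white cells. If that sample is missed, they should be drawn as early as possible and before the first follow-up scan. Record the draw date in every case.

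Add to section 2.4 that a value drawn after the first follow-up scan is flagged and left out of the main determinant analysis, with a sensitivity analysis that includes it. Reconcile the minimum stay in the Abstract with section 2.2.1, Table 1 and the short-stay schedule, so that it is clear who is exposed.

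The cost is a few sentences and three tests added to the first request form. The assays are the same, and no extra blood draw is needed when the admission sample is used. The downside is a few missing values among short-stay patients whose sample was late. The sensitivity analysis shows whether leaving those values out matters.

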### 2.3.2. Muscle mass

In order to obtain reliable and consistent measurements, all ultrasonography will be done by an ultrasonographist that is trained to perform the measurements proposed. For the measurements, a linear probe of 5 cm width will be used. Frequency of the beam will be set on 12 MHz.

Patients should not have had any physical exercise in the 30 minutes before the measurement. Muscles should be completely relaxed and patients should be placed in the supine position, with hips in neutral position and knees fully extended. The dominant leg will be taken for the measurements. To calculate the relative muscle thickness values, the total length of muscle will be noted.

Ultrasonographic data of the four bellies of the quadriceps muscle (rectus femoris, vastus lateralis, vastus medialis, vastus intermedius) will be taken. Measuring points will be specified according to the propositions of the SARCUS-working group [19]. Muscle thickness, fascicle length, pennation angle, muscle cross-sectional area and echo-intensity of all muscles listed will be taken.

The first measurement will be taken as early as possible within 48 hours after admission at the latest. Follow-up measurements will be taken according to the type of ward the patient is admitted to. For patients that are expected to be hospitalized for a limited time (<5 days), the follow-up measurement will be done 3 days after initial measurement. For patients that are expected to be hospitalized for a longer time (>7 days), measurements will be repeated 7

days after initial measurement, to be repeated after another 7 days as long as the patient is hospitalized.

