## Abstract

Sarcopenia is a geriatric syndrome defined as progressive and generalized age-related muscle loss with decline in muscle mass and muscle function (either strength or performance). It is closely related to adverse outcomes such as frailty, reduced quality of life, increased risk of falling, more frequent hospitalisations and higher mortality. Acute sarcopenia is the decline of muscle mass and function following acute disease or hospitalisation, sufficiently to meet the criteria of sarcopenia.

Objectives: To assess the effect of hospitalisation and acute illness on muscle mass and function, and to assess which other factors contribute to the development of acute sarcopenia.

Study design and main outcome measures: This study is a prospective multicenter observational study. Patients admitted to acute geriatric wards of different European centers and hospitalised for at least 5 days will be included. Measurements of muscle mass will be performed via ultrasound. Measurements of muscle function will be done by hand grip strength using Jamar dynamometer and by gait speed using the 4-meter walking test, when feasible. Other parameters will be measured via file study, laboratory investigations or validated questionnaires. Activity levels during hospitalisation will be measured through pedometers.

Anticipated results: Decline of muscle mass and muscle characteristics secondary to hospitalisation. We also expect an association with reasons of hospitalisation, pre-existing conditions, laboratory results and nutritional status prior to hospitalisation on the decline in muscle parameters.

Conclusions: This study seeks to gain knowledge of the development of acute sarcopenia and its contributing factors.

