## **1.2. Hypothesis**

Hospitalisation and acute illnesses will negatively affect both muscle mass and muscle function and will hereby contribute to the development of acute sarcopenia. We hypothesize that hospitalisation due to an elevated degree of inflammation will lead to more severe decrease of muscle mass and muscle function than hospitalisation due to non-inflammatory reasons. Furthermore, certain pre-existing conditions are supposed to increase the risk of acute sarcopenia.

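### Operator, machine, gain and depth may change between a patient's repeat scans, and masking to earlier values is not specified, although the primary endpoint is within-patient change

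*Combined protocol and SAP*

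**What the plan says.** Section 1.1 makes the main outcome a change over time: "The primary endpoint is the change of characteristics of muscle mass in function of time since admission". The direction is announced twice, in the Abstract ("Anticipated results: Decline of muscle mass and muscle characteristics secondary to hospitalisation") and in section 1.2 ("Hospitalisation and acute illnesses will negatively affect both muscle mass and muscle function").

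Section 2.3.2 sets out how scans are made. On the person scanning, its one rule is that "all ultrasonography will be done by an ultrasonographist that is trained to perform the measurements proposed". On equipment, "a linear probe of 5 cm width will be used" and "Frequency of the beam will be set on 12 MHz". On technique, "patients should be placed in the supine position, with hips in neutral position and knees fully extended". Muscles are to be relaxed, the dominant leg is used, and exercise is ruled out for the preceding 30 minutes. On location, "Measuring points will be specified according to the propositions of the SARCUS-working group".

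Five parameters are taken for each of four quadriceps bellies, echo-intensity among them. The follow-up scan comes 3 days after the first for short expected stays. For longer stays it comes at 7 days and then weekly.

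Neither this section nor any other requires the same operator or machine for a patient's repeat scans, fixes gain or depth, provides for recording who scanned on which machine, or says whether the person measuring can see earlier values. No check of agreement within or between operators is planned.

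**The concern.** A difference between two scans of one patient is free of operator and device effects only if operator, device and settings are the same on both occasions. The plan leaves that to chance, across several hospitals. The Introduction itself acknowledges that standardising muscle ultrasound in older people has been a major difficulty.

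Three things are at stake:

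- **Precision.** A switch of operator or machine adds error to the change score, over intervals short enough that true change may be small.
- **Echo-intensity.** This is a brightness reading, so a change of gain between visits alters it directly. A gain change that was never recorded cannot be undone in the analysis.
- **Expectation.** If the person measuring knows the earlier value and expects decline, readings may drift in that direction. In a single observational cohort, the overall mean change has no comparison group against which such drift would show.

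Operator and machine identity may be impossible to recover if not noted at the scan, so the gap is hard to repair after data collection.

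**Working it through.** The documents give no sample size, SD, reliability or measurement error, so there is no figure of the plan's own to reproduce. Everything below rests on assumed inputs.

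**Inputs (all assumed).** Reliability (ICC) of a single scan is 0.95 when one operator does both scans, and 0.90 or 0.85 when operators differ. The SD of true change is 0.3 or 0.5 of the baseline SD. Baseline variance is set to 1. Operator effects are taken as random and unrelated to visit.

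**Step 1: measurement variance of a change score**, 2 × (1 − ICC):

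- same operator: 2 × 0.05 = 0.10
- different operators, ICC 0.90: 2 × 0.10 = 0.20
- different operators, ICC 0.85: 2 × 0.15 = 0.30

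Measurement variance is therefore 2 to 3 times larger when operators switch.

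**Step 2: total variance of change**, adding true-change variance (0.3² = 0.09 or 0.5² = 0.25):

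| True-change SD | Same operator | Switch, ICC 0.90 | Switch, ICC 0.85 |
|---|---|---|---|
| 0.3 | 0.19 | 0.29 | 0.39 |
| 0.5 | 0.35 | 0.45 | 0.55 |

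**Step 3: interval width relative to no switching**, the square root of the variance ratio. When half the pairs switch, the variance is the average of the same-operator and switched values.

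| True-change SD | ICC | Every pair switches | Half switch |
|---|---|---|---|
| 0.3 | 0.90 | √(0.29/0.19) = 1.24 | √(0.24/0.19) = 1.12 |
| 0.3 | 0.85 | √(0.39/0.19) = 1.43 | √(0.29/0.19) = 1.24 |
| 0.5 | 0.90 | √(0.45/0.35) = 1.13 | √(0.40/0.35) = 1.07 |
| 0.5 | 0.85 | √(0.55/0.35) = 1.25 | √(0.45/0.35) = 1.13 |

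Intervals are 13% to 43% wider if every pair switches and 7% to 24% wider if half do.

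**Cross-check with another parametrisation.** Put true-change SD at 1, same-operator error SD at 0.5 or 1.0, and operator SD between 0.25 and 1.0. The variance of change is 1 + 2 × (error SD)², plus 2 × (operator SD)² when every pair switches. The sample size needed for equal precision is then multiplied by 1.04 (3.125/3) at the mildest and 2.33 (3.5/1.5) at the worst. The cost can be trivial or large, depending on values the documents do not supply.

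**Reading bias.** No input in the documents bears on its size. A purely hypothetical case shows only how it behaves. With no true change, a mean shift of 0.1 SD of change and a two-sided 5% test, the chance of a significant result is 17% at n = 100 and 52% at n = 400. Unlike operator noise, bias matters more as the sample grows.

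**The case against.** The strongest reply is that section 2.3.2 standardises a good deal, and that the rest is inferred from silence. Much of this stands.

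- A reader might infer that training is the only safeguard. It is not: probe, frequency, position, leg, rest and measuring points are all set. What stays open is operator, machine, gain, depth and masking.
- A reader might infer that earlier values will be on view. The documents do not say so. They do not describe how values are displayed, whether images are stored, or how each parameter is read. The supportable statement is that masking is not specified.
- A reader might take 43% as the expected loss. It is the top of an assumed range and requires every pair to switch. The plan gives no indication of how often switching would occur.
- A reader might infer that operator switching would create a false decline. Random operator error costs precision and weakens associations; it does not by itself move the mean.
- A reader might infer that no comparison in the study could escape reading bias. Section 1.2 hypothesises a contrast of inflammatory with non-inflammatory admissions, and a bias common to all follow-up scans would largely cancel there, unless readers also act on the admission reason.

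Two further defences carry less weight. The cited working-group paper may cover machine settings, but section 2.3.2 invokes it only for measuring points, and its content cannot be checked here. The singular noun for the operator could be read as one person, but the study spans several hospitals and nothing says one operator per patient.

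It is also fair to say that preferring the same operator may help that person recall earlier readings. With four bellies and five parameters there are up to 20 values per scan, so withholding them should still help.

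**Conclusion.** The point holds as a specific, inexpensive gap. The plan standardises much of the scan but does not hold operator, machine, gain and depth constant within a patient, does not provide for recording operator or machine, and does not specify masking, while its primary endpoint is within-patient change with decline expected.

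The loss of precision is about 13% to 43% in interval width if every pair switches operator and about 7% to 24% if half do. That rests entirely on the assumed reliabilities and true-change SDs, and no stated precision target is breached. Any reading bias is unsized; it would affect mean change most and the contrast by admission reason least. The documents do not support saying that the result will be biased, only that the plan does not guard against it.

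**What to change.** Add to section 2.3.2:

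> All scans of a patient use the same machine and a saved preset (gain and depth, in addition to the 12 MHz already set), and the same operator where possible. Operator and machine are recorded at each scan. Earlier values are not available to the operator when measurements are made.

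Add to section 2.4 a sensitivity analysis of the primary endpoint restricted to pairs of scans with the same operator and the same machine.

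The cost is protocol wording, two identifier fields, minor rota planning, and a data-entry form in the Access database that does not show earlier values. No extra staff or central reader is needed. The change reduces expectation bias but does not remove it, because the operator still knows that a scan is a follow-up. The Discussion states that no data are yet available, so on the document's own account the rule can be in place before measurement begins.

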### **2.2. Subjects**

#### **2.2.1. Inclusion criteria**

Patients admitted between the 1st of November 2018 until the 31th of October 2019 will be eligible for inclusion. Included wards for admission are: internal medicine, acute geriatrics, orthogeriatrics and rehabilitation. Age limit will be set on 65 years and older.

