## Appendix

**Table 1:** Inclusion and exclusion criteria for patient participation

Inclusion criteria	Exclusion criteria
Admitted from 01/11/2018 – 31/10/2019	Dialysis
65 years or older	Previous/actual stroke
	Actual hypo- or hyperthyroidism.
	Oedema of the lower limbs
	Severely dehydration
	Systemic connective tissue disorders 
 
• Polyarteritis nodosa and related conditions
 
• Other necrotizing vasculopathies
 
• Systemic lupus erythematosus
 
• Dermatopolymyositis
 
• Systemic sclerosis – scleroderma
 
• Other systemic involvement of connective tissue
 
• Systemic disorders of connective tissue in diseases classified elsewhere
 

	Myositis
	Calcification and ossification of muscle
	Systemic atrophies primarily affecting the central nervous system 
 
• Huntington's disease
 
• Hereditary ataxia
 
• Spinal muscular atrophy and related syndromes
 
• Systemic atrophies primarily affecting central nervous system in diseases classified elsewhere
 
• Postpolio syndrome
 

	Demyelinating diseases of the central nervous system 
 
• Multiple sclerosis
 
• Other acute disseminated demyelination
 
• Other demyelinating diseases of central nervous system
 

	The chronic use of oral corticosteroids

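### The dominant leg is scanned with no exception for injury or surgery, and the listed data cannot show whether the scanned thigh was the affected one

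*Combined protocol and SAP*

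**What the plan says.** - **Leg scanned.** Section 2.3.2: "The dominant leg will be taken for the measurements". No exception is given for a fractured or operated leg. Five characteristics are taken from each of the four quadriceps bellies on that leg.
- **Who is scanned.** Section 2.2.1: "Included wards for admission are: internal medicine, acute geriatrics, orthogeriatrics and rehabilitation".
- **Who is excluded.** Section 2.2.2 lists "Pitting oedema of the legs (due to heart failure, anasarca oedema, renal failure or liver cirrhosis" as its bracketed causes, and gives as the reason that "fluid shifts could influence the ultrasound measurement results". Table 1 in the Appendix states only "Oedema of the lower limbs", with no cause. Neither list names leg fracture, leg injury or leg surgery.
- **What the scans feed.** Section 1.1: "The primary endpoint is the change of characteristics of muscle mass in function of time since admission". The planned determinants are "reason of hospitalisation, comorbidities and laboratory data". Section 1.2 expects that "hospitalisation due to an elevated degree of inflammation will lead to more severe decrease of muscle mass and muscle function" than admission for non-inflammatory reasons.
- **What is recorded.** Section 2.3.1 records the main reason for admission and the CIRS-G, which has one combined musculoskeletal and skin category. Section 2.3.2 adds muscle length. Sections 2.3.1 to 2.3.6 do not list leg dominance, leg scanned, or side, site or date of an injury or operation.

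**The concern.** The endpoint is meant to measure muscle lost during acute illness and hospital stay. In a thigh that has recently been injured or operated on, the image can also change because blood or fluid collects or clears, or because surgery has altered the tissue. Swelling that resolves after the baseline scan would look like muscle loss; swelling that appears after baseline would hide it.

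The protocol already accepts the principle, since it excludes leg oedema because fluid can affect the scan. It does not carry that reasoning over to local causes in the limb being measured, although two of its ward types can be expected to admit such patients.

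Two things are at stake: the estimate of change itself, and the comparison by reason for hospitalisation, where any local effect would sit mainly among injury admissions. Real muscle loss from not using an injured limb is not treated as error here.

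**Working it through.** The plan gives no sample size, standard deviation or expected change, so there is no figure of its own to reproduce. The check is of the text, followed by a labelled illustration.

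1. **Exposure.** Orthogeriatrics and rehabilitation are 2 of the 4 ward types in section 2.2.1. This counts ward types, not patients: no ward mix is given, rehabilitation is not said to be orthopaedic, and the Abstract mentions only acute geriatric wards.

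2. **Exclusions.** Table 1 has 11 entries: dialysis, stroke, thyroid disease, leg oedema, severe dehydration, connective tissue disorders, myositis, muscle calcification or ossification, systemic atrophies, demyelinating disease, and chronic oral corticosteroids. Leg fracture, injury or surgery is named in 0 of 11. The paresis exclusion in section 2.2.2 is neurological and does not cover orthopaedic injury.

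3. **Dependence on one leg.** 4 bellies × 5 characteristics (thickness, fascicle length, pennation angle, cross-sectional area, echo-intensity) = 20 values per scan, all from the same thigh. There is no second leg to compare with.

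4. **Timing.** Baseline is within 48 hours of admission. The first repeat is 3 days later for expected stays under 5 days and 7 days later for expected stays over 7 days. In those two groups, an operation performed between the two scans is at most 3 or 7 days old at the first repeat. This says nothing about operations before baseline, and expected stays of 5 to 7 days have no stated schedule. It shows that recent surgery can fall between scans; it does not bound the bias.

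5. **Can affected scans be found later?** At patient level, often yes, from the main reason for admission. At leg level, no: this needs both the side affected and the side scanned. File study, which the Abstract plans as a data source, may recover the side of an operation. It recovers the side scanned only if dominance or image side happens to have been noted, which the plan does not require.

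6. **Illustration (every input assumed).** Let *p* be the share of patients with a recent leg injury or operation, *s* the share of those whose scanned thigh is the affected one, and *d* the net local effect on the measured change, in percent of baseline. Shift in mean change = *p* × *s* × *d*.
   - *p* = 0.10, *s* = 0.5, *d* = 10: 0.10 × 0.5 × 10 = 0.5 percentage points.
   - *p* = 0.40, *s* = 0.5, *d* = 20: 0.40 × 0.5 × 20 = 4.0 percentage points.
   - Within a group made up only of such patients (*p* = 1): 0.5 × 10 = 5 to 0.5 × 20 = 10 points, against none in a group without them.

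   The sign may be positive or negative. Injuries below the knee need not alter the thigh, which lowers *s*. The last line shows why the comparison by reason for admission is more exposed than the overall mean. Without the side recorded, *s* cannot be estimated from the study's own data.

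**The case against.** The other side has real points.

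- **The reason for admission is recorded.** A reader might infer that affected patients will be invisible in the data. The documents do not support that: most injury admissions can be identified, and a crude analysis leaving all of them out needs no new field. What is missing is leg-level information, and any injury or operation that was not the main reason for admission.
- **There are partial barriers.** Read literally, Table 1's leg oedema entry covers much swelling present at entry, and the required scan position (supine, hips neutral, knees straight, muscles relaxed) may be out of reach for some injured patients. Neither clearly deals with haematoma, surgical change or swelling that begins after baseline, and failing to reach the position is not an exclusion criterion.
- **The inflammation hypothesis.** A reader might infer that local thigh change must bias the contrast in section 1.2, whichever side injury admissions fall on. That does not follow. If the groups are formed on the admission CRP or white cell count in section 2.3.1, injury patients may fall in both. Only the comparison by reason for hospitalisation clearly concentrates the effect.
- **No size is shown.** This stands. The counts above describe the text, not the impact, and effects of opposite sign may partly cancel.
- **Disuse loss may be part of what is studied.** This also stands, and it is why these patients stay in the main analysis.
- **The cited ultrasound guidance may cover injured limbs.** It was not available. Section 2.3.2 invokes it only for the measuring points.

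**Conclusion.** The point holds. Followed as written, the plan lets local change in an injured or operated thigh enter the primary endpoint, and the listed data cannot reliably separate those scans by leg afterwards. The likely consequence is distortion of the comparison by reason for hospitalisation, with a smaller effect on overall change; for the inflammation comparison it depends on a grouping rule the plan does not give.

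Size and direction are unknown. The 0.5 to 4.0 point range rests wholly on assumed values and only shows how the three unknowns combine. The conclusion itself assumes no more than that some patients from the listed wards will have a recent injury or operation affecting the dominant thigh.

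This should be corrected before data collection, because the side scanned is trivial to note at the bedside and may not be recoverable later. Confidence is medium, since the documents do not show how many patients are involved.

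**What to change.** **Section 2.3.2, add:** The leg scanned is recorded at every scan. The side, site and date of any recent leg injury or operation, within a stated look-back window and including events after baseline, are recorded. Scans of an affected thigh are flagged.

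**Section 2.4, add:** The analysis of change and the comparison by reason for admission are repeated without flagged scans. A patient whose baseline scan is flagged contributes no change; where only a later scan is flagged, only that scan is left out. This presupposes a stated analysis of within-patient change, which section 2.4 does not yet contain; that is a separate gap.

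**Sections 2.2.2 and Table 1:** reconcile which leg oedema excludes a patient, since one gives systemic causes and the other none.

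Switching to the unaffected leg is not needed: it would remove genuine disuse loss and tie the side scanned to the reason for admission.

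**Cost:** about four database fields (leg scanned; side, site and date of injury or operation), a flag derived from them, and one sensitivity analysis. No extra scans. The sensitivity analysis will have fewer patients and will also drop real disuse loss, so a difference from the main result would point to the affected thighs without proving that the cause is a measurement artefact.
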